# 6.3 Quality of Life (QoL)

#### 6.3.1 Functional Assessment of Cancer Therapy-P (FACT-G) and Kidney Symptom Index (FKSI)

Patient-reported functional status will be assessed with prostate cancer subscales of the Functional Assessment of Cancer Therapy-General (FACT-G) (See appendix for form). The FACT-G is a 28-item questionnaire that uses 5-point Likert-type response choices (0 = not at all; 1 = a little bit; 2 =somewhat; 3 = quite a bit; 4 = very much). It will take less than 10 minutes to complete the questionnaire. The Trial Outcome Indices (TOI) also will be utilized to measure the summed functional well-being, physical well-being [103, 104]. A 5-point deterioration in the FACT-G TOI between pre-treatment and at post treatment or at year 1 will be considered clinically significant [105].

The FACT-G and FKSI will be given on Day 1 and 28 similar to several other quality of life studies [106],[82], [85]

The FKSI is a 15 question validated symptom index for kidney cancer patients which has been used in several metastatic renal cell cancer studies [106]. This scale focuses on symptoms predominantly related to kidney cancer such as energy, fatigue, pain, bone

pain, weight loss, shortness of breath, cough, fever, hematuria. This subscale of the FKSI-DRS was validated in another study as well [107]

The first analysis of change in QOL from baseline to 8 weeks will only be performed on patients who are still alive at 8 weeks. Changes in QOL will be also analyzed using all available data at baseline, 8, 16, 24, and 36 weeks with semiparametric generalized estimating equations (GEE).

Additionally, similarly we will also compare the percentage of patients with an effect size for the change in FKSI (FKSI) scores between pre-treatment and post treatment which will allow us to compare the percentage of patients whose functional status remains more similar to baseline levels.

#### 6.3.2 EQ-5D

The EQ-5D is a patient self-administrated questionnaire that takes approximately 5 minutes to complete (See appendix for form). The first part consists of 5 items covering 5 dimensions including: mobility, self care, usual activities, pain/discomfort, and anxiety/depression. Each dimension can be graded on 3 levels: 1-no problems, 2-moderate problems, and 3-extreme problems. Health states are defined by the combination of the leveled responses to the 5 dimensions, generating 243 health states to which unconsciousness and death are added.

The 5-item index score is transformed into a utility score between 0, "Worst health state," and 1, "Best health state." The index score or the cost-utility equation can be used in the quality adjusted survival analysis depending on the health state(s) of interest.

Additionally the EQ 5D is utilized to establish health state utility which is used in costeffectiveness analysis to calculate quality adjusted life years. This is the recommended health state utility form used in the United Kingdom and approved by the National Institute for Clinical Excellence (NICE) and has been used to establish health state utility and metastatic renal cell cancer patients. Unfortunately, to our knowledge there is no health state utilites established for patients receiving IL-2, much less HD-IL-2. Likewise , there is no data for metastatic renal cell carcinoma patients within the setting of SABR treatment.

The EQ-5D will also be available in the Spanish language.

#### 6.4 Cost effectiveness data collection:

Health care utilization data needed to assess costs will be obtained from treatment records. Additionally, in order to assess the treatment related indirect costs and patient out of pocket costs, a form will be administered at the first available follow up visit after completion of radiation treatment (see Appendix VII).

Hospitalizations:. For hospitalizations with physician billing records, impatient physician costs will be estimated by applying Medicare payment rates under the RBRVS-based Medicare Fee Schedule to billed procedures in the physician billing records. This is of great importance given that these patients will be admitted to the intensive care unit.

Treatment Cost: Direct costs of radiation treatment including consultation, simulation, treatment planning, and treatment delivery. Patient bills related to treatment will be obtained and estimated by total billed charges adjusted by facility-specific cost-to-charge ration from Medicare cost reports as described above.

Emergency Room visits: The date of ER visit and name of the facility, and whether the ER visit resulted in a hospital admission. ER costs will be estimated using IL-2 STU012013-041, [name], Form A3, Mod 49, 05-20-19 Medicare average payment rates for facility and physician charges, using the merged MEDPAR and MBS data as described above.

Physician and Clinic Visits: The date of the visit, the name of the physician or physician clinic, and the service provided (physician exam, lab test, physical therapy, etc.). Costs for physician and clinic visits will be calculated based on billing records obtained for such visits, using Medicare payment rates for procedures indicated in the clinic billing records.

Medications: Prescription drugs used, including dosage strength and frequency of administration. Information about name, dose, and frequency of all prescription medications will be recorded. The medications used by the study patients will be assigned an NDC drug code. Unit costs for these drugs will be estimated as the "AWP" price published in the Red Book less 15%. Outpatient drug costs will be calculated by multiplying unit cost by the number of pills used per day times the length of time the patient received the medication. Note that costs of drugs administered through a clinic (e.g., reimbursed under Medicare Part B) are included under "clinic visit costs" and impatient drug costs are included under "inpatient facility costs." For example: Cost estimated for the HD-IL-2 infusions will be based on Medicare allowable utilizing the appropriate J code and associated facility charges for administration of HD-IL-2.

# 7.0 ADVERSE EVENTS

#### 7.1 SABR

The contraindications and adverse events for SABR are mostly related to the treatment site and its radiation dose tolerance, as discussed in detail in section 4.1

- 7.1.1 Contraindications: None
- 7.1.2 Special Warnings and Precautions for Use: N/a
- 7.1.3 Interaction with other medications: None
- 7.1.4 Adverse Reactions: Sites-specific. Please see section 4.1

#### 7.2 HD IL-2

The standard treatment regiment for HD IL-2 which has been proven to be safe at UTSW over the past years will be used for this protocol (as detailed in section 4, Appendix B and C). For the most recent safety update, please refer to the current Study Agent Prescribing Information in the company website: http://www.proleukin.com/assets/pdf/proleukin.pdf

7.2.1 Contraindications

HD IL-2 is contraindicated in patients with a known history of hypersensitivity to IL-2 or any component of the HD IL-2 formulation. HD IL-2 is contraindicated in patients with an abnormal thallium stress test or abnormal pulmonary function tests and those with organ allografts. Retreatment with HD IL-2 is contraindicated in patients who have experienced the following drug-related toxicities while receiving an earlier course of therapy:

- Sustained ventricular tachycardia (≥5 beats)
- Cardiac arrhythmias not controlled or unresponsive to management
- Chest pain with ECG changes, consistent with angina or myocardial infarction
- Cardiac tamponade
- Intubation for >72 hours
- Renal failure requiring dialysis >72 hours
- Coma or toxic psychosis lasting >48 hours
- Repetitive or difficult to control seizures
- Bowel ischemia/perforation
- GI bleeding requiring surgery

#### 7.2.2 Special Warnings and Precautions for Use

Because of the severe adverse events which generally accompany HD IL-2 therapy at the recommended dosages, thorough clinical evaluation should be performed to identify patients with significant cardiac, pulmonary, renal, hepatic, or CNS impairment in whom HD IL-2 is contraindicated. Patients with normal cardiovascular, pulmonary, hepatic, and CNS function may experience serious, life threatening or fatal adverse events. Adverse events are frequent, often serious, and sometimes fatal.

Should adverse events, which require dose modification occur, dosage should be withheld rather than reduced (See "**DOSAGE AND ADMINISTRATION**" section, "**Dose Modifications**" subsection of the manufacturer's prescribing information).

HD IL-2 has been associated with exacerbation of pre-existing or initial presentation of autoimmune disease and inflammatory disorders. Exacerbation of Crohn's disease, scleroderma, thyroiditis, inflammatory arthritis, diabetes mellitus, oculo-bulbar myasthenia gravis, crescentic IgA glomerulonephritis, cholecystitis, cerebral vasculitis, Stevens-Johnson syndrome and bullous pemphigoid, has been reported following treatment with IL-2.

All patients should have thorough evaluation and treatment of CNS metastases and have a negative scan prior to receiving HD IL-2 therapy. New neurologic signs, symptoms, and anatomic lesions following HD IL-2 therapy have been reported in patients without evidence of CNS metastases. Clinical manifestations included changes in mental status, speech difficulties, cortical blindness, limb or gait ataxia, hallucinations, agitation, obtundation, and coma. Radiological findings included multiple and, less commonly, single cortical lesions on MRI and evidence of demyelination. Neurologic signs and symptoms associated with HD IL-2 therapy usually improve after discontinuation of HD IL-2 therapy; however, there are reports of permanent neurologic defects. One case of possible cerebral vasculitis, responsive to dexamethasone, has been reported. In patients with known seizure disorders, extreme caution should be exercised as HD IL-2 may cause seizures.

Patients should have normal cardiac, pulmonary, hepatic, and CNS function at the start of therapy. (See "**PRECAUTIONS**" section, "**Laboratory Tests**" subsection of manufacturer's prescribing information). Capillary leak syndrome (CLS) begins immediately after HD IL-2 treatment starts and is marked by increased capillary permeability to protein and fluids and reduced vascular tone. In most patients, this results in a concomitant drop in mean arterial blood pressure within 2 to 12 hours after the start of treatment. With continued therapy, clinically significant hypotension will occur. In addition, extravasation of protein and fluids into the extravascular space will lead to the formation of edema and creation of new effusions.

Medical management of CLS begins with careful monitoring of the patient's fluid and organ perfusion status, as described in Section 4, Appendices B and C, in accordance with the established and standard practice guidelines followed at UTSW. This is achieved by frequent determination of blood pressure and pulse, and by monitoring organ function, which includes assessment of mental status and urine output. Hypovolemia is assessed by catheterization and central pressure monitoring.

Flexibility in fluid and pressor management is essential for maintaining organ perfusion and blood pressure. Correction of hypovolemia may require large volumes of IV fluids but caution is required because unrestrained fluid administration may exacerbate problems associated with edema, in particular leading to pulmonary edema. With extravascular fluid accumulation, edema is common and ascites, pleural or pericardial effusions may develop.

Management of these events depends on a careful balancing of the effects of fluid shifts so that neither the consequences of hypovolemia (e.g., impaired organ perfusion) nor the consequences of fluid accumulations (e.g., pulmonary edema) exceed the patient's tolerance.

Clinical experience has shown that early administration of dopamine (1 to 5 µg/kg/min) to patients manifesting capillary leak syndrome, before the onset of hypotension, can help to maintain organ perfusion particularly to the kidney and thus preserve urine output. Weight and urine output should be carefully monitored. If organ perfusion and blood pressure are not sustained by dopamine therapy, the dose of dopamine can be titrated as described in section 4 and in Appendix C, to 5mcg/kg/min to maintain SBP equal to or greater than 90 mm Hg, or add phenylephrine hydrochloride 20 mg/500 ml NS at 1 mcg/kg/min and titrate to 1.5 mcg/kg/min. (See "ADVERSE REACTIONS" section below). Prolonged use of pressors, either in combination or as individual agents, at relatively high doses, may be associated with cardiac rhythm disturbances. If there has been excessive weight gain or edema formation, particularly if associated with shortness of breath from pulmonary congestion, use of diuretics, once blood pressure has normalized, has been shown to hasten recovery. NOTE: Prior to the use of any product mentioned, the physician should refer to the package insert for the respective product.

HD IL-2 treatment should be withheld for failure to maintain organ perfusion as demonstrated by altered mental status, reduced urine output, a fall in the systolic blood pressure below 90 mm Hg or onset of cardiac arrhythmias (See "**DOSAGE AND ADMINISTRATION**" section 4.2 and "**Dose Modifications**" subsection 4.3). Recovery from CLS begins soon after cessation of HD IL-2 therapy. Usually, within a few hours, the blood pressure rises, organ perfusion is restored and reabsorption of extravasated fluid and protein begins. Kidney and liver function are impaired during HD IL-2 treatment. Use of concomitant nephrotoxic or hepatotoxic medications may further increase toxicity to the kidney or liver. Mental status changes including irritability, confusion, or depression which occur while receiving HD IL-2 may be indicators of bacteremia or early bacterial sepsis, hypoperfusion, occult CNS malignancy, or direct HD IL-2-induced CNS toxicity. Alterations in mental status due solely to HD IL-2 therapy may progress for several days before recovery begins. Rarely, patients have sustained permanent neurologic deficits (See "**Drug Interactions**" section below).

Exacerbation of pre-existing autoimmune disease or initial presentation of autoimmune and inflammatory disorders has been reported following HD IL-2 alone or in combination with interferon. Hypothyroidism, sometimes preceded by hyperthyroidism, has been reported following HD IL-2 treatment. Some of these patients required thyroid replacement therapy. Changes in thyroid function may be a manifestation of autoimmunity. Onset of symptomatic hyperglycemia and/or diabetes mellitus has been reported during HD IL-2 therapy.

HD IL-2 enhancement of cellular immune function may increase the risk of allograft rejection in transplant patients.

# 7.2.1 Drug Interactions

HD IL-2 may affect central nervous function. Therefore, interactions could occur following concomitant administration of psychotropic drugs (e.g., narcotics, analgesics, antiemetics, sedatives, tranquilizers).

Concurrent administration of drugs possessing nephrotoxic (e.g., aminoglycosides, indomethacin), myelotoxic (e.g., cytotoxic chemotherapy), cardiotoxic (e.g., doxorubicin) or hepatotoxic (e.g., methotrexate, asparaginase) effects with HD IL-2 may increase toxicity in these organ systems. The

safety and efficacy of HD IL-2 in combination with any antineoplastic agents have not been established. In addition, radiographic contrast material should be avoided one week pre and post HD IL-2 therapy, unless absolutely necessary, to avoid inducing an allergic reaction.

In addition, reduced kidney and liver function secondary to HD IL-2 treatment may delay elimination of concomitant medications and increase the risk of adverse events from those drugs.

Hypersensitivity reactions have been reported in patients receiving combination regimens containing sequential high dose HD IL-2 and antineoplastic agents, specifically, dacarbazine, cis-platinum, tamoxifen and interferon-alfa. These reactions consisted of erythema, pruritus, and hypotension and occurred within hours of administration of chemotherapy. These events required medical intervention in some patients.

Myocardial injury, including myocardial infarction, myocarditis, ventricular hypokinesia, and severe rhabdomyolysis appear to be increased in patients receiving HD IL-2 and interferon-alfa concurrently.

Exacerbation or the initial presentation of a number of autoimmune and inflammatory disorders has been observed following concurrent use of interferon-alfa and HD IL-2, including crescentic IgA glomerulonephritis, oculo-bulbar myasthenia gravis, inflammatory arthritis, thyroiditis, bullous pemphigoid, and Stevens-Johnson syndrome.

Although glucocorticoids have been shown to reduce HD IL-2-induced side effects including fever, renal insufficiency, hyperbilirubinemia, confusion, and dyspnea, concomitant administration of these agents with HD IL-2 may reduce the antitumor effectiveness of HD IL-2 and thus should be avoided

Beta-blockers and other antihypertensives may potentiate the hypotension seen with HD IL-2.

# 7.2.2 Adverse Reactions

#### >10%:

Cardiovascular: Hypotension (71%; grade 4: 3%), peripheral edema (28%), tachycardia (23%), edema (15%), vasodilation (13%), supraventricular tachycardia (12%; grade 4: 1%), cardiovascular disorder (11%; includes blood pressure changes, HF and ECG changes) Central nervous system: Chills (52%), confusion (34%; grade 4: 1%), fever (29%; grade 4: 1%), malaise (27%), somnolence (22%), anxiety (12%), pain (12%), dizziness (11%) Dermatologic: Rash (42%), pruritus (24%), exfoliative dermatitis (18%) Endocrine & metabolic: Acidosis (12%; grade 4: 1%), hypomagnesemia (12%), hypocalcemia (11%) Gastrointestinal: Diarrhea (67%; grade 4: 2%), vomiting (19% to 50%; grade 4: 1%), nausea (19% to 35%), stomatitis (22%), anorexia (20%), weight gain (16%), abdominal pain (11%) Hematologic: Thrombocytopenia (37%; grade 4: 1%), anemia (29%), leukopenia (16%) Hepatic: Hyperbilirubinemia (40%; grade 4: 2%), AST increased (23%; grade 4: 1%) Neuromuscular & skeletal: Weakness (23%) Renal: Oliguria (63%; grade 4: 6%), creatinine increased (33%; grade 4: 1%) Respiratory: Dyspnea (43%; grade 4: 1%), lung disorder (24%; includes pulmonary congestion, rales, and rhonchi), cough (11%), respiratory disorder (11%; includes acute respiratory distress syndrome, infiltrates and pulmonary changes) Miscellaneous: Antibody formation (66% to 74%), infection (13%; grade 4: 1%)

# 1% to 10%:

Cardiovascular: Arrhythmia (10%), cardiac arrest (grade 4: 1%), MI (grade 4: 1%), ventricular tachycardia (grade 4: 1%)

Central nervous system: Coma (grade 4: 2%), stupor (grade 4: 1%), psychosis (grade 4: 1%) Gastrointestinal: Abdomen enlarged (10%)

Hematologic: Coagulation disorder (grade 4: 1%; includes intravascular coagulopathy)

Hepatic: Alkaline phosphatase increased (10%)

Renal: Anuria (grade 4: 5%), acute renal failure (grade 4: 1%)

Respiratory: Rhinitis (10%), apnea (grade 4: 1%) Miscellaneous: Sepsis (grade 4: 1%)

#### <1% (Limited to important or life-threatening):

Allergic interstitial nephritis, anaphylaxis, angioedema, asthma, atrial arrhythmia, AV block, blindness (transient or permanent), bowel infarction/necrosis/perforation, bradycardia, bullous pemphigoid, capillary leak syndrome, cardiomyopathy, cellulitis, cerebral edema, cerebral lesions, cerebral vasculitis, cholecystitis, colitis, crescentic IgA glomerulonephritis, Crohn's disease exacerbation, delirium, depression (severe; leading to suicide), diabetes mellitus, duodenal ulcer, encephalopathy, endocarditis, extrapyramidal syndrome, hemorrhage (including cerebral, gastrointestinal, retroperitoneal, subarachnoid, subdural), hepatic failure, hepatitis, hepatosplenomegaly, hypertension, hyperuricemia, hypothermia, hyperthyroidism, inflammatory arthritis, injection site necrosis, insomnia, intestinal obstruction, intestinal perforation, leukocytosis, malignant hyperthermia, meningitis, myocardial ischemia, myocarditis, myopathy, myositis, neuralgia, neuritis, neuropathy, neutropenia, NPN increased, oculobulbar myasthenia gravis, optic neuritis, organ perfusion decreased, pancreatitis, pericardial effusion, pericarditis, peripheral gangrene, phlebitis, pneumonia, pneumothorax, pulmonary edema, pulmonary embolus, respiratory acidosis, respiratory arrest, respiratory failure, rhabdomyolysis, scleroderma, seizure, Stevens-Johnson syndrome, stroke, syncope, thrombosis, thyroiditis, tracheoesophageal fistula, transient ischemic attack, tubular necrosis, ventricular extrasystoles

# 7.3 Adverse Event Monitoring

Adverse event data collection and reporting, which are required as part of every clinical trial, are done to ensure the safety of subjects enrolled in the studies as well as those who will enroll in future studies using similar agents. Adverse events are reported in a routine manner at scheduled times during a trial. Additionally, certain adverse events must be reported in an expedited manner to allow for optimal monitoring of subject safety and care.

All subjects experiencing an adverse event, regardless of its relationship to study drug, will be monitored until:

- the adverse event resolves or the symptoms or signs that constitute the adverse event return to baseline;
- > any abnormal laboratory values have returned to baseline;
- there is a satisfactory explanation other than the study drug for the changes observed

# **Acute Adverse Events**

An adverse event is defined as any untoward or unfavorable medical occurrence in a human research study participant, including any abnormal sign (for example, abnormal physical exam or laboratory finding), symptom, clinical event, or disease, temporarily associated with the subject's participation in the research, whether or not it is considered related to the subject's participation in the research. Adverse events occurring through the time period of the start of treatment through the first follow up occurring 12 weeks post treatment will be considered acute adverse events. All acute adverse events will be assessed and reported as per below.

#### Late Adverse Events

Adverse effects occurring in the time period from the end of acute monitoring, to 3 years post treatment for progression or death (whichever comes first), will be defined as late adverse events. These events will include all adverse events reported directly to a member of the study team and will be captured, assessed, graded and reported as appropriate.

In addition, the study team will review encounters in a select specialty category relevant to study endpoints. These select specialties include hospitalizations, medical oncology, and radiation oncology records and will be limited in scope based on categorization of events (GU/GI) and also the type of records that will be queried (hospitalizations, medical oncology, and radiation oncology).

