The SABR prescription dose will be delivered to the periphery of the planning target volume (PTV, see below for definitions). Investigators will have discretion in choosing from either of the biologically equivalent dose levels using one or three fractions, although a single fraction is preferred over three fraction treatments. Treating physician will have further discretion in selecting the number and location of sites to treat if >6 sites of disease are present. Maximum number of lesions treated is deemed as feasible per the treating radiation oncologist. Physician's will be **REQUIRED** to leave at least one site of disease for the purpose of measuring a radiographic response (see section 6.1) at a non-treated site, as this is part of the primary endpoint. If left untreated, this site can be treated once patient meets the definition of progressive disease (PD) (see section 6). To clarify the definition of "site", each site is an area or organ with active extracranial disease (</=3 in the liver = one site and </=3 in the lung= one site) identified by CT scan, or PET/CT, within 4 weeks prior to initiation of SBRT (up to 2 contiguous vertebral metastasis will be considered a single site of disease). For example: a patient with 4 right axillary lymph nodes, L1-L2 bone metastasis, 3 right lung lesions, 1 left lung lesion, 2 liver lesions, and T2-T3 bone metastasis would be defined as having 6 sites of disease. Preference should be given to the largest feasible disease site, symptomatic sites and sites where palliative and preventative (i.e. to prevent a pathologic fracture in weight bearing bone, impending cord compression, impending SVC compression etc.) indications are applicable. The gross target/tumor volume (GTV) should be at least 2cm^3 in size, corresponding to roughly a 1.5 cm diameter tumor. This is to ensure that adequate tumor volume and therefore adequate tumor cells (roughly 10^8 -10^9 cells/cm^3 [96]) are killed for antigen presentation. Treating physicians should choose their dose based on established planning guidelines at their center including their ability to respect normal tissue tolerance listed below. It is not required that all targets be treated with the same dose fractionation. A dose from the following table should be used:

	Total Cumulative Dose Encompassing 95% of Planning					
	Target Volume (Gy)					
Number of	Protocol Compliant Minor Deviation * MinorDeviation					
Fractions						

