#### 4.4 Duration of Follow Up

Subjects will be followed for ten years or death (although findings will be analyzed and reported at a median follow up of 2-4 years), whichever occurs first. Subjects removed from treatment for unacceptable adverse events will be followed until resolution or stabilization of the adverse event. The follow-up will be every 8 weeks (+/- 2 Weeks) from study registration with imaging studies and physical exam every 8 weeks for the first eight months, then every 12 weeks (+/- 2 Weeks) until two years, then every four months thereafter for a total of five years, and then every six months (+/- 1 month) for a total of ten years. See section 5.0 for detail.

Subjects who show progressive disease will be followed for survival and will no longer strictly adhere to study calendar. QOL questionnaires will be completed every 4 months until 1 year after treatment.

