#### 5.3 Follow-up Procedures

Subject will be followed every eight-ten weeks (+/- 2 Weeks) starting from the date of registration for the first eight months, then every 12 weeks until 18 months and then every sixteen weeks for another three years and then every three – six months for the next five years. Thereafter at the discretion of the treating physician. The following procedures will be performed at each follow up:

- Physical exam, vital signs
- Hematology
- Serum chemistries
- QoL questionnaire (every other follow up)
- Blood collection for correlative immunologic studies (see section 9.0) Radiographic imaging
  - $\circ$   $\,$  CT chest, abdomen and pelvis with IV contrast, if soft tissue metastasis
  - Bone scan if bone lesion was present and detected by the baseline Bone scan
  - MRI, if necessary to confirm CT/bone scan findings, at the discretion of radiologist

	Pre-study	Cycle 1 , Day15 (+/- 5)	Cycle2, Day30 (+/- 14)	Cycle2, Day37 (+/- 14)	Months 1-8: q8 Weeks	Months 8-18: q12 Weeks	Months 18- 120: 3-6 months
Assessment	Х				Х	Х	Х
Informed Consent	Х						
Vital Signs	Х	Х	Х	Х	Х	Х	Х
History and PE	Х				Х	Х	Х
Performance Status	Х				Х	Х	X
Toxicity (include DLT) Evaluations	Х				Х	Х	Х
Bone Scan	Х				X*	X*	Х
CT Chest, Abd, pelvis w/ Contrast	Х				Х	Х	Х
Biopsy of metastatic lesion	Χ^				X@		
CBC with diff	Х	X 	X 	X 	Х	Х	Х
Basic Chemistry	X	X 	X 	X 	Х	Х	Х
Comprehensive chemistry	Х			Х	X&		
Blood collection for Immune Assays	Х			Х	X#	X#	X#
QOL Questionnaires	Х			X%	X%	X%	X%
Cardiac Stress Test	Х						
PFT	X						

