#### 6.2 Safety/tolerability

Analyses will be performed for all subjects having received at least one fraction of SABR and one cycle of HD IL-2. The study will use the CTCAE version 4.0 for reporting of non-hematologic adverse events (http://ctep.cancer.gov/reporting/ctc.html) and modified criteria for hematologic adverse events (Appendix #/letter).

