# 7.6 Steps to Determine If an Adverse Event Requires Expedited Reporting to the SCCC DSMC and/or HRPP.

Step 1: Identify the type of adverse event using the NCI Common Terminology Criteria for Adverse Events (CTCAE v4).

Step 2: Grade the adverse event using the NCI CTCAE v4.

Step 3:Determine whether the adverse event is related to the protocol therapy Attribution categories are as follows:

- Definite The AE is clearly related to the study treatment.
- Probable The AE *is likely related* to the study treatment.
- Possible The AE may be related to the study treatment.
- Unrelated The AE is clearly NOT related to the study treatment.

Note: This includes all events that occur within 30 days of the last dose of protocol treatment. Any event that occurs more than 30 days after the last dose of treatment and is attributed (possibly, probably, or definitely) to the agent(s) must also be reported accordingly.

Step 4: Determine the prior experience of the adverse event.

Expected events are those that have been previously identified as resulting from administration of the agent. An adverse event is considered unexpected, for expedited reporting purposes only, when either the type of event or the severity of the event is not listed in:

- the current known adverse events listed in the Agent Information Section of this protocol;
- the drug package insert;
- the current Investigator's Brochure

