# 11.3 Data Analyses Plans

This is a single-arm Phase II trial of SABR and HD IL-2 for mRCC patients. PFS and OS, will be estimated using the Kaplan-Meier approach along with the 95% confidence interval. Exact binomial method will be used to calculate the response rate, toxicity and the corresponding 95% confidence interval. One-sample log-rank test [121] will be used to test if the survival endpoints such as OS or PFS are significantly different from those in the historical control reported in McDermott et. al [35].

Generalized estimating equation (GEE) analysis will be conducted to test if the median number of spots in Elispot of the PBMC collected from patients are significantly different over time (before starting of treatment and after SBRT, at 8 weeks and six months). T-Cell proliferation SI will also be evaluated in the same manner.

HRQol, CEA and quality adjusted survival time analysis is described in Section 10.

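### Late toxicity is likely understated: the late adverse-event window appears to close at progression, and section 11.3 then reports a crude binomial proportion that takes no account of time at risk

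*Combined protocol and SAP*

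**What the plan says.** Section 7.3 splits adverse events by time. Those from the start of treatment "through the first follow up occurring 12 weeks post treatment will be considered acute adverse events". Those from then "to 3 years post treatment for progression or death (whichever comes first), will be defined as late adverse events". As written, the second sentence does not parse cleanly. Read naturally, it lists three possible ends of the window (3 years, progression, death) and takes the earliest.

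Section 4.4 adds: "Subjects who show progressive disease will be followed for survival and will no longer strictly adhere to study calendar".

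For the analysis, section 11.3 says only: "Exact binomial method will be used to calculate the response rate, toxicity and the corresponding 95% confidence interval". The denominator comes from section 6.2: "Analyses will be performed for all subjects having received at least one fraction of SABR and one cycle of HD IL-2". No section gives a time-to-event or competing-risk method for toxicity, or a time at risk for late events.

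Two other places point towards continued capture. The Time and Events table has a row "Toxicity (include DLT) Evaluations" marked in every follow-up column, the last covering months 18 to 120. Section 7.6 requires reporting of events more than 30 days after the last dose if they are at least possibly attributed to the agent(s), and names no cut-off at progression.

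**The concern.** A binomial proportion is a fair summary when every patient is watched for the same period. Here the period would end at progression for most patients. They stay in the denominator as event-free, while an event after progression falls outside the defined late set. The bias can only be downward, and the exact interval does not show it, because that interval reflects sampling error and not unobserved time.

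Toxicity is a secondary objective (section 2.2.7). The stopping rule in section 7 compares Grade 3-5 toxicity with literature rates, and undercounted late events would weaken that comparison. The dose-constraint tables in section 4.1.3.2 list Grade 3 or higher endpoints such as stenosis, fistula, myelitis and fracture, and the text there discusses airway occlusion from radiation fibrosis. Section 4.1.1 also lets the deliberately spared site be irradiated once progression is met. On the natural reading of section 7.3, that is the moment at which late capture closes.

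**Working it through.** The plan states no late-toxicity rate, median PFS or onset distribution, so it has no figure of its own to reproduce. The check asks how far a proportion captured only before progression falls below one captured until death or 3 years.

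**Inputs**
- Window (section 7.3): from a = 12 weeks = 84/30.4375 = 2.76 months to b = 36 months.
- Median OS: section 1.1 puts five-year survival in metastatic disease below 10%. An exponential curve at 10% has rate -ln(0.10)/60 = 0.0384 per month and median ln 2/0.0384 = about 18 months. A more favourable 30 months is taken as an alternative.
- Median PFS: assumed at 4, 6, 9, 12 and 24 months.
- Late risk: assumed 15% over the window if nobody died or progressed, with constant hazard H = -ln(0.85)/(36 - 2.76) = 0.00489 per month.
- Patients: 33, the maximum in section 11.2.
- Simplifications: all clocks start together, survival curves are exponential, and progression does not change H.

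**Formula**

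For observation that ends with median m, and L = ln 2/m:

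C(m) = [H/(H + L)] × exp(-L a) × [1 - exp(-(H + L)(b - a))]

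With m = median OS, this is the cumulative incidence with death competing and capture continued past progression. With m = median PFS, it is the expected crude proportion when capture stops at progression. The understatement is C(OS)/C(PFS).

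**Numbers**
- Median OS 18: L = 0.0385, so C = 0.1127 × 0.899 × 0.764 = 7.7%, or 2.55 expected events in 33.
- Median OS 30: C = 9.9%, or 3.28 events in 33.
- Median PFS 6: L = 0.1155, so C = 0.0406 × 0.727 × 0.982 = 2.9%. The ratio to 7.7% is 2.7.

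| Median PFS (months) | Crude proportion | Events in 33 | Understated, OS 18 | Understated, OS 30 | Progression-free at 36 months |
|---|---|---|---|---|---|
| 4 | 1.7% | 0.56 | 4.6-fold | 5.9-fold | 0.2% |
| 6 | 2.9% | 0.96 | 2.7-fold | 3.4-fold | 1.6% |
| 9 | 4.5% | 1.49 | 1.7-fold | 2.2-fold | 6.3% |
| 12 | 5.8% | 1.92 | 1.3-fold | 1.7-fold | 12.5% |
| 24 | 9.0% | 2.98 | not applicable | 1.1-fold | 35.4% |

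**Sensitivity to onset**

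The ratio of the integrals of h(t) S_OS(t) and h(t) S_PFS(t) over the window was taken for four shapes of h: constant, rising linearly, and declining as exp(-t/6) and exp(-t/12) in months. At median PFS 6 it runs from 1.7 to 4.1 (OS 18) and 1.9 to 5.7 (OS 30). At median PFS 12 it runs from 1.15 to 1.5 and 1.3 to 2.1.

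**Sensitivity to durable responders**

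Suppose responders have a median of 24 months (the response duration in section 6.1) and non-responders an assumed median PFS of 3 to 6 months. Over both OS values and all four shapes, the ratio is 1.4 to 4.3 at a 23% response rate and 1.3 to 2.9 at 36.8%.

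**Full reporting**

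If every treatment-attributed event after progression is reported and counted, the ratio goes to 1.

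**The case against.** A reader might infer that capture flatly ends at progression. The documents do not go that far. The toxicity row runs to month 120, section 7.6 keeps later attributed events reportable, and section 4.5 continues follow-up after removal from therapy. Section 6.1.4.5 considers a fracture at a treated site as treatment-related toxicity, and section 7.3 follows events already under way. Section 4.4 loosens the calendar after progression but does not abolish contact. The sentence in section 7.3 could even be read as extending past progression. What remains is that none of these passages redefines the late-event set or supplies a time at risk. Section 7.6 concerns expedited reporting and speaks of agent(s), which may not cover SABR.

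A reader might also infer that late injury is understated several-fold. That needs a median PFS of about 6 months or less, or late-weighted onset, and the documents establish neither. Setting the crude rate against a 15% risk in which nobody dies also exaggerates the gap: at median PFS 6 months, 15%/2.9% is about 5-fold, where the like-for-like ratio is 2.7. Loss to death is a competing event, not undercounting.

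Nor do the documents make late toxicity a Phase III criterion: section 11.2 decides on response alone. With 33 patients the exact 95% intervals are 0 to 10.6% for no events and 0.1 to 15.8% for one. Both contain 7.7% and 9.9%, so a low crude rate could not by itself establish safety. These points limit the weight of the finding but do not remove the bias.

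**Conclusion.** The point holds in a limited form. On the natural reading of section 7.3, together with sections 4.4 and 11.3, the planned late-toxicity rate is biased downward, and other sections conflict on whether collection continues. The size cannot be fixed from the documents. Under constant hazard, exponential curves, death competing and an assumed median OS of 18 to 30 months, it is about 1.3- to 1.7-fold at median PFS 12 months, 2.7- to 3.4-fold at 6 months and 4.6- to 5.9-fold at 4 months. It approaches none if attributed events are fully reported after progression. For any exponential median PFS below 36 months, most patients would not be progression-free for the whole window. The primary response endpoint is unaffected. The change should be made because it is cheap and the safety summary would otherwise mislead.

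**What to change.** 1. In section 11.3, report late toxicity as cumulative incidence by the Aalen-Johansen method, with death as a competing event and censoring at the last toxicity assessment, and show the number at risk. Keep the exact binomial for acute toxicity.
2. Reconcile section 7.3 (late events), section 4.4, the Time and Events table and section 7.6. Recording of Grade 3 or higher events attributed to an irradiated site should not stop at progression but run to 3 years or death. Flag events that occur after another therapy starts.

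Both parts are needed. A new estimator alone would still censor patients at progression, which may be informative.

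The cost is a few sentences of protocol and analysis text, and modest extra record review within follow-up that section 4.4 already runs to ten years or death. The drawback is that attribution after progression needs judgement, particularly once other treatment has begun.
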